Enrollment in HIV Care as a Couple. Consent will be confirmed to enter care as a study participant. The staff member will explain that the positive partner is eligible for HIV-related treatment regardless of their CD4 count and will remind the couple that the positive partner is eligible for care, according to the national guidelines, should they not want to enter the study. A Study Nurse will review again the benefits and risks associated with PrEP, and the preventative benefits of ARV use with regard to reduction in HIV transmission to the negative partner. In addition, a month's supply of condoms will be provided to the couple, and staff will inform them that they can return for more condoms as needed, and they will be counseled on the preventative benefits of condom use and sexual abstinence. The positive partner will then be referred to the CTC Medical Officer who will conduct a medical assessment and following national guidelines, establish a treatment regimen for the positive partner. In many cases, families share a cellphone. In order to be able to communicate with participants and add a layer of protection to confidentiality, we will provide an inexpensive cell phone to each participant. In

addition, both partners will be asked their preferred alternative communication methods in the event we are unable to reach them using the provided study phones or they are unable to make it to the study office for the 6-, 12-, and 18-month study visits.

The Negative Partner will be Offered PrEP.

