
Formative Research

Prior to conducting the intervention, we will conduct formative research to explore the knowledge, attitudes, and perceived benefits/concerns towards HIV self-testing, pre-exposure prophylaxis (PrEP) use, and early ART among people affected by HIV – both PLWH enrolled in care and seronegative (or unknown status) partners of PLWH – in Kisarawe. This will provide valuable information that will improve intervention implementation.

The specific aims of the formative research component include:

- To develop appropriate counseling tools and strategies regarding HIV self-testing, PrEP, and early ART for the Kisarawe community during the DDCP intervention
- To identify and address challenges/barriers to uptake of HIV self-testing, PrEP, and early ART so these can be addressed during counseling and while raising community awareness
- To use perceived concerns and benefits to improve intervention implementation

To evaluate these aims, we will conduct up to 45 qualitative, in-depth interviews (IDIs) with different target sub-populations recruited from the Kisarawe CTC, including people who are currently receiving ART (up to 15 interviews), people who are in care but not on ART (up to 15 interviews), and HIV-negative people whose partners are in care (up to 15 interviews). Participants will be selected by purposive sampling through the CTC in Kisarawe District Hospital, Kisarawe Town. We will target adult HIV-positive Kisarawe community members engaged in services at the CTC, stratifying by type of services received: either engaged in care (receiving monthly ART) or not in care (registered at CTC but not receiving monthly ART, likely waiting for CD4 count to drop below national guideline threshold). We will also try to sample approximately equal numbers of men and women, for equal gender representation. In addition, we will use chain/snowball sampling among CTC clients to reach our other target sub-group: HIV-negative members of couples engaged in CTC services. In addition, we will hold four focus groups (1 for males in care, 1 for females in care, 1 for males who are seronegative partners, and 1 for females who are seronegative partners) with 5-10 participants per group to understand social norms and confirm findings.

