Data Structure: There are two key unique features of the primary data for this proposal. First, because couples are enrolled in the study, there is inherent nesting of two individuals within each couple. Second, the measurement design leads to repeated measurements outcomes for some of the aims. Given the aims of the study, many of the outcomes will be evaluated using descriptive statistics. However, issues such as nesting and repeated measurements will be carefully considered. For example, for the first aim, uptake will be reported by each individual within the couple, and the descriptive statistics will be reported both at the individual level within the couple and at the aggregate couple level. For the outcomes that will be evaluated using inferential statistical analyses, the nested data structures (e.g., repeated measurements within couples) will be addressed using mixed-effects regression models (MRMs; e.g.).⁸¹ These highly flexible models accommodate variability in the number/spacing of outcome measurements, and they readily accommodate linear and non-linear outcome distributions (e.g., dichotomous, count). **Outcome Distributions & Individual Trajectories:** Prior to analysis, each outcome will be carefully inspected to determine the most appropriate distribution for modeling. Likewise, for outcomes with repeated measurements, the trajectory for each participant on each outcome will be plotted using “spaghetti plots”.⁸² These plots will illustrate the level of and variability in each outcome, along with patterns of change over time. **Model Building & Estimation:** Singer and Willett’s (2003)⁸³ model building approach will be used to specify fixed and random effects. The MRMs will be performed using MLwiN software.⁸⁴ Due to the relatively modest sample size for some of the analyses, the models will also be performed using Bayesian MCMC-based estimation⁸⁵ in MLwiN. This simulation-based approach utilizes a large number of iterations – each informing the next – to produce an empirically-based sampling distribution for each parameter. For example, rather than a single point estimate of the parameter of interest, the MCMC-based provides the magnitude, precision, and variability of the parameter estimates. **Attrition & Missing Data:** Individuals or couples who drop out of clinic care will be retained, when possible, in ongoing research measurement according to Intention-to-treat principles.⁸⁶ Some research data will inevitably be missing, and the methods recommended by Schafer and Graham⁸⁷ will be used to evaluate missing data assumptions and guide the subsequent analyses. Given few missing data and evidence supporting a MAR mechanism, the procedures detailed above will be utilized with all available data. Given non-trivial missing data and evidence supporting MAR, multiple imputation for longitudinal data will be used to provide complete data.⁸⁸ Finally, given non-trivial missing data and evidence suggesting NMAR, pattern mixture models will be used to control the missing data.⁸²

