
Evaluation of Specific Aims & Associated Hypotheses

AIM 1 - We hypothesize that the majority of couples (GT ~ 50%) will utilize the HIV self-test kits and share their results with their partner. To evaluate the factors associated with uptake of HIV self-testing, a single level logistic regression model with a logit link function will be performed. The outcome will be the HIV self-testing status (0 = did not use self-test, 1 = used self-test). Demographic variables (e.g., age & gender) will be evaluated as predictors of self-testing uptake, with results focusing on ORs, and corresponding 95% CIs.

AIM 2 - We hypothesize that a large proportion of serodiscordant couples who present to the study referral office (GT ~ 70%) will engage in care together, have higher rates of adherence and retention than individually enrolled clients, and have a reduction in risk behaviors for HIV transmission from baseline to 18-month follow up. For this aim, there are repeated measurements of retention in care and adherence (level-1) nested within positive partners (level-2). A dichotomous predictor variable at the individual level (i.e., level-2) will test for differences in the log-odds of treatment retention between those enrolled in care as a couple and those enrolled in routine clinic services. The adherence outcome will be analyzed in a similar manner. For this outcome, there are several indicators of medication adherence. First, for the positive member of the couples, self-reports of ARV adherence will be obtained at 6, 12, and 18 months. Second, individuals on ARV are expected to return to the clinic each month to have the prescription refilled. Third, for individuals in the study, viral load tests will be obtained at 18 months allowing us to assess viral suppression as a marker for medication adherence. For the

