first outcome, self-reported ARV adherence, the three repeated measurements will be nested within the positive partners. The unconditional model will estimate the rate of, and variability in, ARV adherence across participants. Based on inspection of "spaghetti plots," subsequent level-1 growth models will be specified to test for change in the rate of ARV adherence over time. For the second outcome, each positive individual from the study and from the CTC will have 18 monthly measurements of ARV refill status (i.e., 0 = Not Refilled, 1 = Refilled). This will be modeled as described above, with the level-2 dichotomous indicator testing for a difference in the average log-odds of adherence for those enrolled as a couple and those enrolled in routine clinic care. Given the large number of measurements per individual, alternative specifications are possible, and this will be guided by inspection of the spaghetti plots. For the third outcome, CD4 counts at 18 months will be compared using a single-level regression model to test for differences between those enrolled as a couple and those enrolled in routine services. For the fourth outcome, sexual frequency, condom use, and sex in the context of ARV or PrEP will be estimated. Using a mixed-effects model, predictor variables related to risk will be added to the model. These variables will also be considered for entry as time-varying covariates (i.e., entry at level-1) or as aggregative, couple-specific predictors.

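### Aim 2 names 18-month viral suppression as its third adherence indicator, but the third outcome it models is 18-month CD4 with no stated baseline adjustment, and suppression has no threshold or explicit analysis

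*Combined protocol and SAP*

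**What the plan says.** Under AIM 2 in Evaluation of Specific Aims, the adherence indicators are self-report at 6, 12 and 18 months, monthly prescription refill, and viral load: "Third, for individuals in the study, viral load tests will be obtained at 18 months allowing us to assess viral suppression". The same paragraph says in general terms: "The adherence outcome will be analyzed in a similar manner", referring back to the retention model with its couple-versus-routine indicator.

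The outcomes are then taken in order. The first is self-report. The second is refill, where "each positive individual from the study and from the CTC will have 18 monthly measurements of ARV refill status". The third changes marker: "For the third outcome, CD4 counts at 18 months will be compared using a single-level regression model to test for differences" between couple and routine enrolment. The fourth concerns sexual behaviour.

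The section Clinical Data from Care and Treatment Center says that CTC2 records CD4, that viral load will be added at the 18-month study visit, and that other patients' data will allow suppression to be compared. The Clinical item under Measures collects CD4 and viral load results from clinic records only where they exist, and adds a study blood draw for viral load at the final interview for positive partners in the cohort. Data Structure in the Analysis Plan says that "many of the outcomes will be evaluated using descriptive statistics", without naming this one.

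**The concern.** The marker collected to show adherence biologically has no cut-off, coding or stated analysis, while a marker absent from the list of adherence indicators receives the formal group comparison in its place. A threshold not fixed in advance can be chosen after the data are seen.

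The CD4 comparison has its own difficulty. CD4 at 18 months depends on CD4 at the start and on how long a person has been on ART. Neither is named in the regression, and the groups are not randomised. The AIM 2 hypothesis is comparative: better adherence and retention than individually enrolled clients. Self-reported adherence is taken only from positive partners in couples, so among the adherence items the explicit group contrast is refill, with CD4 next in the sequence. A CD4 difference could then be credited to dyadic care when it was present at entry.

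**Working it through.** **1. The two lists side by side (AIM 2).**

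| Position | Indicator listed | Outcome modelled |
|---|---|---|
| First | Self-reported ARV adherence | Self-reported ARV adherence |
| Second | Monthly refill | Monthly refill |
| Third | 18-month viral load (suppression) | 18-month CD4 |

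The first two match and the third does not.

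**2. Search for a suppression analysis.** Viral load or suppression appears in the opening summary, Clinical Data from Care and Treatment Center, Measures and AIM 2. These give the timing, the purpose and an intention to compare. None gives a threshold, outcome coding, model or comparator window.

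**3. Can the groups differ at the start?** The opening summary and Sampling of Households recruit couples both through self-testing and from patients already in care at the CTC, and fix no split. Under Enrollment in HIV Care as a Couple, "the positive partner is eligible for HIV-related treatment regardless of their CD4 count". So starting CD4 and ART duration can differ between the groups. No index date says when 18 months begins for a CTC comparator.

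**4. Direction of the bias.** In a linear model with no effect of dyadic care:

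expected unadjusted difference (couple minus routine) = b1 × (gap in baseline CD4) + b2 × (gap in ART duration).

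If treatment regardless of CD4 raises starting CD4 in the couple group, the first term is positive. If routine patients have been treated longer and CD4 rises with time on ART, the second is negative. The documents give none of b1, b2 or the two gaps, so neither size nor sign follows.

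**5. Precision.** Precision of Estimates and Statistical Power has no figure for either 18-month comparison, so there is nothing to reproduce. The following is illustration only, using that section's planning number of 50 individuals and assumed suppression rates, with 95% CI = p ± 1.96 × √(p(1−p)/50):

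- p = 70%: ±12.7 points, 57% to 83%
- p = 80%: ±11.1 points, 69% to 91%
- p = 90%: ±8.3 points, 82% to 98%

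For 50 study positives against an assumed 50, 100 or 250 CTC patients with a viral load, two-sided 5% power for 85% versus 70% is 0.43, 0.58 or 0.69. A formal comparison of suppression would be weak.

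For CD4 with 50 against 50 and 80% power, the detectable difference is (1.96 + 0.84) × √((1−r²)(1/50 + 1/50)). That is 0.56 SD unadjusted (r = 0) and 0.40 SD if baseline CD4 correlates at an assumed r = 0.7. Adjustment would then help precision as well as bias.

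**The case against.** The best defence is that the two markers serve different purposes. The planned viral load draw is for study individuals, whereas CTC2 holds CD4 for clinic patients. Viral load could be a within-study marker under the descriptive default, and CD4 the between-group clinical comparison. The outcome list is not confined to adherence, since its fourth item is sexual behaviour, and the study is exploratory by design. This reading is coherent, but the plan does not state it, and the stated intention to compare suppression with clinic patients cuts against it.

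Four stronger readings are tempting and should not be drawn.

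- A reader might infer that the retention-type model cannot handle one viral load per person. The couple-versus-routine term is a person-level contrast. With one binary result each, the model reduces to ordinary logistic regression and the contrast remains estimable. What is missing is the definition and the statement.
- A reader might infer that retention and refill rest on an equally unadjusted contrast. Those are mixed models. The Analysis Plan describes a model-building step for their fixed effects, and AIM 2 leaves room for alternative specifications of the refill model. That step concerns mixed models and supplies no covariates for the single-level CD4 regression. It is also true that naming one term does not exclude others.
- A reader might take the comparators to be untreated, from the Formative Research description of patients "registered at CTC but not receiving monthly ART, likely waiting for CD4 count to drop below national guideline threshold". That describes interview recruitment before the intervention. Nothing shows that such patients make up the 18-month comparator.
- A reader might treat patchy clinic records as a problem for viral load only. The qualifier under Measures covers CD4 as well.

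**Conclusion.** The point holds. The third adherence indicator and the third modelled outcome are different markers, and suppression has neither a threshold nor an explicit analysis. Both facts can be read directly from the text.

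The CD4 part is a risk of confounding, not a demonstrated bias. It assumes that the regression is run with only its named term and that the groups differ in starting CD4 or time on ART, which the recruitment routes allow but the documents do not quantify. No magnitude can be given. AIM 2 never calls CD4 an adherence measure, so the documents do not support saying that the plan presents it as one. The concern is that its position invites that reading. This should be fixed before analysis; it does not undermine the study's design.

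**What to change.** - **Reconcile the two AIM 2 lists**, saying what role each marker has.
- **Suppression:** analyse it at 18 months as an adherence outcome, with a threshold and visit window stated in advance, as a proportion with 95% CI in study positives. Compare with CTC patients, by single-level logistic regression or descriptively, only as far as CTC viral loads are available.
- **CD4:** list it at 18 months as a separate clinical outcome, adjusted for baseline CD4 and, where recorded, time since ART start. Do not interpret it as an adherence effect.
- **Index date:** define the start of the 18 months for CTC comparators, and use it for the monthly refill records too.
- **Availability:** report by group how many people have each marker. The COVID-19 section pauses extraction of CTC2 card data and moves remaining surveys to the phone, which could thin the data further; it does not mention viral load.
- **Missing data:** the existing rule can carry over: "Given non-trivial missing data and evidence supporting MAR, multiple imputation for longitudinal data will be used to provide complete data".

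The cost is low for the text and for suppression, since the test is already planned. It is moderate for CD4. CTC2 holds CD4 and pharmacy data, and study records track CD4, but the Clinical item lists no ART start date. First prescription pick-up could stand in for people who start during the study, but not for those already treated unless earlier records are abstracted. Some patients will lack baseline CD4 or a start date and must be imputed or dropped from the CD4 model.

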This is an ideal study setting. The intervention strategy we propose is based on our extensive experience conducting large-scale HIV prevention trials in Tanzania for over 17 years in collaboration with Muhimbili University. Over the past 8 years we have collected extensive data on HIV risk and

household characteristics from NIMH Project Accept – a multi-site community randomized Phase III trial assessing the efficacy of community-based HIV voluntary counseling and testing. We have mapped and enumerated all households in the district, done qualitative research, characterized HIV risk factors (behavioral and biologic), done cost-analyses, worked successfully with the local communities and health system, established a collaboration with the PEPFAR-funded AIDS treatment centers, and established a rural research infrastructure with experienced intervention and research staff. Our specific AIMS evaluate 4 key strategic goals, including:

1. HIV Self-Testing for Stable Couples: (a) assess the acceptability, safety, and factors associated with uptake of HIV self-testing; and (b) determine the proportion of clients testing positive for HIV via self-testing who engage in care.
2. Dyadic Engagement of Serodiscordant Couples in Care & Prevention: (a) establish the proportion of serodiscordant couples who will enroll in HIV care as a dyad, (b) determine the effect of dyadic care enrollment on retention and adherence, and (c) assess reduction in risk of acquiring HIV infection for the negative partner.
3. Pre-Exposure Prophylaxis (PrEP): (a) establish the proportion and characteristics of HIV negative clients in a serodiscordant relationship who opt to take PrEP, (b) determine how engaging in ARV treatment by the positive partner affects PrEP utilization by the negative partner, and vice versa, and (c) Identify patterns and correlates of risk reduction strategies that couples in care utilize over time (abstinence, ARV for positive partner, PrEP for negative partner, condom use).
4. Operational: (a) determine Dyadic-based Diagnosis, Care, & Prevention (DDCP) program cost and economic efficiency, (b) compare DDCP to clinic-based and mobile VCT with regard to cost and efficiency for testing and linkage to care, and (c) assess the feasibility, acceptability, safety, and utility of using biometric data to track service utilization.

B. BACKGROUND AND SIGNIFICANCE

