This will be in the form of Truvada (™) which is a fixed-dose combination tablet combining 200mg FTC (emtricitabine) and 300mg TDF (tenofovir disoproxil fumarate). It is manufactured by Gilead Sciences, and Gilead has offered to donate the full supply of Truvada needed for the study. FTC is a nucleoside reverse transcriptase inhibitor (NRTI) and tenofovir is a nucleotide reverse transcriptase inhibitor (NtRTI). One pill is taken daily. In the Partners in Prevention trial there was an observed 75% (95% CI: 55-87%, P<.0001) reduction in incidence with this regimen in Kenya and Uganda.¹⁷ Clients will be advised that they need to have an HIV test conducted regularly to assure that there is no breakthrough infection of HIV, and to promptly report any adverse events or side-effects. All participants eligible for PrEP will have their blood drawn for Creatinine testing to ascertain kidney function. We will also screen PrEP candidates for Hepatitis B prior to starting PrEP. If participants test Hepatitis B positive, they will be provided an additional test (for ALT) to ascertain liver function. If kidney or liver function is poor, the participant will not be eligible for PrEP. For those who test Hepatitis B negative, the vaccination will be offered. Follow up visits will be scheduled at the CTC for the positive partner as per standard of care in Tanzania and the Study Center for the negative partner for a clinical assessment and renewal of prescriptions of ARV (and PrEP as indicated). With consent we shall also track the clinical records of study participants to assess the uptake of ARV & PrEP, and the refilling of prescriptions, clinical signs and symptoms, regular CD4 counts, and HIV test results of the negative clients. At each entry to the clinic a data collector will take a fingerprint scan of study participants and indicate in the records (via tablet) the reason for the visit, and at each visit participants will be assessed for any negative social, psychological, or physical events. All adverse events and unintended consequences will be promptly reported to the study PI for follow up. All pregnancy-related adverse events will be reported to the Antenatal Pregnancy Registry. As PrEP is a relatively new HIV prevention tool, information about PrEP, such as best practices for monitoring safety and adherence, is constantly being updated as data emerges from other studies. We plan to monitor this information and update the study protocol accordingly. We will submit amendments to the IRB for any protocol changes that occur.

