AIM 3 - We hypothesize that a moderate proportion of HIV negative partners will utilize PrEP (~ 30%), that PrEP utilization among HIV negative partners will be associated with lack of ARV use by positive partners, and ARV use by positive partners will be associated with lack of PrEP use by negative partners. To evaluate the factors associated with uptake of PrEP, a single level logistic regression model with a logit link function will be performed. Demographic variables such as age and gender will be evaluated as predictors of PrEP uptake, with the results focusing on the odds ratios, and corresponding 95% confidence intervals, for these variables. To evaluate association between ARV and PrEP utilization within couples, two main models will be performed. For the first, the outcomes will be variables related to the use of PrEP. Likewise, for the second, the outcomes will be variables related to the use of ARV. These outcomes will be evaluated using MRMs as described above. Because each outcome is specific to one member of the couple (i.e., the negative partner for PrEP and the positive partner for ARV), the data will have a two level structure with repeated measurements (level-1) nested within couples (level-2). At the repeated measurements level of the model, the partner's ARV or PrEP status for the preceding time period will be entered as a time-varying covariate. For example, for the PrEP outcome, the positive partner's ARV status will be entered at level-1, and this will test for differences in the use of PrEP for negative partners whose positive partners were on ARV versus not on ARV. Similarly, for the ARV outcome, the negative partner's PrEP status will be entered at level-1, and this will test for differences in the use of ARV for positive partners whose negative partners were on PrEP versus not on PrEP. More tailored formulations are also possible. For example, introducing a lag between the predictor and outcome could test the extent to which PrEP and ARV status were associated with later initiation of ARV or PrEP. **We hypothesize couples will alternate risk reduction strategies (abstinence, ARV treatment for the positive partner, PrEP for the negative partner, and condom use) but typically maintain at least one strategy.** Each risk reduction strategy will be considered as a separate outcome, with repeated measurements of strategies (level-1) nested within couples (level-2). The model specification will be heavily informed by preliminary evaluation of the spaghetti plots, as described above. These plots will guide tests for patterns of change over time (e.g., linear), specific phases of change, or even invariance over time such that aggregation is justified. After building the mixed-effects model, predictor variables related to the use of abstinence, condoms, ARV, or PrEP will be added to the model. These variables will also be considered for entry as time-varying covariates (i.e., entry at level-1) or as aggregative, couple-specific predictors based on the findings of the previous models. Such a formulation will test for, for example, differences in the use of risk reduction strategies for time periods when the positive partner is on ART versus not on ART. Based on the descriptive statistics and the patterns of use of each individual strategy over time, supplemental analyses will be considered that simultaneously evaluate all of the strategies. For instance, cluster analyses could be used to identify groupings of individuals based on the combination of risk reduction strategies utilized.

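### Aim 3(b) asks which partner's treatment influences the other's, but its two main models omit the outcome's own previous status and leave the lag unclear, so they cannot separate the two directions

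*Combined protocol and SAP*

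**What the plan says.** The specific aims list sets Aim 3(b) as: "determine how engaging in ARV treatment by the positive partner affects PrEP utilization by the negative partner, and vice versa". That is a directional question, asked both ways.

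The analysis section (Evaluation of Specific Aims & Associated Hypotheses, AIM 3) words its hypotheses as associations. The first is that "PrEP utilization among HIV negative partners will be associated with lack of ARV use by positive partners". The second is that "ARV use by positive partners will be associated with lack of PrEP use by negative partners".

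For the within-couple question, "two main models will be performed", one with PrEP as outcome and one with ARV. In both, the partner's "ARV or PrEP status for the preceding time period will be entered as a time-varying covariate". The worked example mentions no lag: "this will test for differences in the use of PrEP for negative partners whose positive partners were on ARV versus not on ARV". Shortly afterwards the plan offers more tailored versions, in which "introducing a lag between the predictor and outcome could test the extent to which PrEP and ARV status were associated with later initiation".

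The Data Structure paragraph of the Analysis Plan and the power section add only random effects. The power calculation uses one level-1 predictor and a random intercept, and it describes the primary test as one of zero time-varying correlation.

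**The concern.** Two models with outcome and predictor exchanged look like tests of two directions. They are not, unless each model also accounts for where its own outcome stood before. A couple in which the positive partner's ARV use led the negative partner to stop PrEP will show ARV and no PrEP together for many months afterwards. A model of ARV on the partner's PrEP then sees less ARV among those on PrEP, although nothing flowed in that direction.

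At stake is the reading of Aim 3(b). A result that positive partners use less ARV when the negative partner is on PrEP could be reported, and programmes could take it as PrEP undermining treatment, when only the opposite influence exists.

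The wording adds a second difficulty. The covariate is said to come from the preceding period, yet a lag is later presented as an additional possibility. The two readings lead to different models with different faults.

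**Working it through.** **1. The plan's own figure.** Inputs from the power section: 50 individuals, 3 occasions, ICC 0.50, OR 4.26, power 0.80.

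- Effective sample = 50 × 3 / (1 + (3 − 1) × 0.50) = 150 / 2 = 75, as stated.
- The baseline rate and exposure split are not given. Assume 37.5 per group, two-sided 0.05, and 17.5% against 47.5%. The OR is (0.475/0.525)/(0.175/0.825) = 4.27.
- The pooled SE is √(2 × 0.325 × 0.675/37.5) = 0.108. The unpooled SE is √((0.175 × 0.825 + 0.475 × 0.525)/37.5) = 0.102. Power = Φ((0.30 − 1.96 × 0.108)/0.102) ≈ 0.80.
- Reading 30% as the overall event rate (15.7% against 44.3%) gives 0.78.

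The figure reproduces, but it is power for an association without direction.

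**2. Concurrent reading.** In a 2×2 table of ARV by PrEP, the odds ratio is ad/(bc) whichever variable is called the outcome. Random-intercept models behave almost the same way. With 50 couples and 17 occasions, the mean coefficients for PrEP on ARV and ARV on PrEP were −0.59 and −0.59 at persistence 0.73, and −0.95 and −0.94 at 0.88. The second model adds essentially nothing.

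**3. Lagged reading, large-sample pattern.** Suppose ARV starts with monthly probability s and stops with probability q, regardless of PrEP. Any ARV difference between PrEP groups at one visit then survives six months in the proportion (1 − s − q)^6. Assumed PrEP rates: stop 12% per month if the partner is on ARV, 3% otherwise; start 3% per month only if the partner is not on ARV. The true reverse OR is 1. Multiplying out the monthly transition probabilities gives:

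| Assumed ARV (month 1; start; stop) and PrEP at month 1 | (1 − s − q)^6 | Concurrent OR, months 6, 12, 18 | Six-month-lag reverse OR |
|---|---|---|---|
| 40%; 6%; 2%; PrEP 50% | 0.92^6 = 0.61 | 0.45, 0.28, 0.22 | 0.61, 0.45 |
| 80%; 20%; 2%; PrEP 30% | 0.78^6 = 0.23 | 0.50, 0.38, 0.32 | about 0.8, 0.76 |
| 90%; 30%; 1%; PrEP 30% | 0.69^6 = 0.11 | 0.54, 0.47, 0.37 | 0.91, 0.90 |
| 40%; 30%; 20%; PrEP 50% | 0.50^6 = 0.02 | about 0.8 throughout | 1.00, 1.00 |

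In the first row, conditioning on own previous-month status in simulated couples gave 0.97 to 1.00. The lagged artefact depends on persistence and vanishes when ARV status changes often.

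**4. Lagged reading at the planned size.** Random-intercept logistic models were fitted to 50 simulated couples. The true one-way effect of previous ARV on PrEP was OR 1/4.26, and PrEP had no effect on ARV. Persistence is the chance of keeping the same status from one occasion to the next, before other effects. Entries are the percentage of data sets with a significant false reverse effect, without → with the outcome's own previous status.

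| Persistence (assumed) | 3 occasions | 17 monthly occasions |
|---|---|---|
| 0.50 | 4.5 → 4.8 | 3.7 → 3.7 |
| 0.73 | 5.8 → 3.3 | 23.0 → 5.0 |
| 0.88 | 16.8 → 2.8 | 62.3 → 5.7 |
| 0.88, couples differing (SD 1) | 31.0 → 5.0 | 52.0 → 9.7 |
| 0.95 | 54.0 → 1.5 | 65.5 → 4.0 |

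The random intercept does not remove the problem. Two qualifications apply.

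- With 17 occasions, persistence 0.88 and no effect in either direction, the models without own status still rejected in 24% to 26% of data sets, around a mean coefficient of zero. Part of the 62.3% is therefore unmodelled serial dependence. The directional part is the shift in the mean coefficient to −0.49.
- The runs above allow treatment histories to build up before the first recorded occasion. Without that run-in, the three-occasion mean at persistence 0.88 was 0.13, so no negative artefact had yet formed.

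**5. What a start/stop model could use.** Under the first row of step 3, ARV use rises from 40% to 67% and averages about 0.55. Expected ARV stops are 50 × 17 × 0.55 × 0.02 ≈ 9, of which about 2.4 occur while the partner is on PrEP. Under the 90% row the latter figure is about 1.

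**The case against.** The strongest reply is that the plan mostly claims association. The AIM 3 hypotheses say so, the primary test is a correlation, and the Overview and the no-control-group rationale describe exploratory, proof-of-concept work. The directional verb appears only in the aims list. This stands as a reason for moderate severity. It does not remove the mismatch, because Aim 3(b) is a named aim and these are its only committed models.

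A second reply is that the optional lag covers the point. It does so only in part. It is not a commitment, and a lag without own previous status leaves the artefact in steps 3 and 4. A model of later initiation would move towards the right conditioning.

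A third reply is that high, fast ARV uptake is the likelier setting. The positive partner is offered immediate access, and some couples come from patients already in care. This also stands: the lagged artefact is then small (about 0.9 in step 3), though the concurrent one remains.

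A reader might infer that the two models always report one association twice. The documents do not support that. It needs concurrent status, and under the lagged reading the coefficients differ (−1.61 and −0.49 at persistence 0.88, 17 occasions). A reader might also infer that a false reverse effect is bound to appear whatever the rates. Steps 3 and 4 show otherwise.

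**Conclusion.** The point holds in limited form. As specified, the two main models cannot separate the directions that Aim 3(b) asks about, and the text does not settle whether the partner covariate is lagged. With concurrent status they give essentially one association. With lagged status, a one-way effect can produce a false reverse finding. With three occasions the false rejection rate runs from about 5% to 54%; with monthly data it runs from about 4% to 66%. Both rise with persistence.

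These sizes rest on assumed persistence, assumed start and stop rates, and a true effect as large as the one the plan powers for. Persistence is plausible for continuing treatments but is not stated.

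The material does not show that a harmful effect of PrEP on ARV use would be reported, only that it could be. Nor does it show that a monthly start/stop model must become the primary analysis. With about 50 couples, the ARV-stop direction would probably have too few events. Severity: should be fixed, in an exploratory study.

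**What to change.** - State in AIM 3 whether the partner's status is concurrent or lagged, and by what interval.
- Report the two present models as one undirected within-couple association, and draw no vice versa conclusion from them.
- For any directional statement, add a supporting analysis that includes the outcome's own previous status, with baseline as the first lag. Alternatively, model starts and stops separately. The data are already planned: clinical records will be tracked "to assess the uptake of ARV & PrEP, and the refilling of prescriptions", and the Clinical item under Measures includes prescription pick-up dates.
- Say in advance that a direction with too few transitions, probably ARV stops, will be reported as not estimable.

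The cost is wording and programming, with no new data. Intervals will be wider. If baseline status is not used as the first lag, 50 × 2 = 100 records remain, the effective sample is 100/1.5 = 66.7, and the power of about 0.80 falls to 0.73–0.76. Some bias remains if couples differ strongly: mean reverse coefficient −0.13 to −0.19, and false rejection up to 9.7%.
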